4.6 Lost to Follow-up

A participant will be considered lost to follow-up if he/she repeatedly fails to return for scheduled visits and is unable to be contacted by the study site.

The following actions must be taken if a participant fails to return to the clinic for a required study visit:

- The site must attempt to contact the participant and reschedule the missed visit as soon as possible. The site should counsel the participant on the importance of maintaining the assigned visit schedule and ascertain whether the participant wishes to and/or should continue in the study.
- Before a participant is deemed lost to follow-up, the investigator or designee must make every effort to regain contact with the subject (where possible, three telephone calls and, if necessary, a certified letter to the subject's last known mailing address or local equivalent methods). These contact attempts should be documented in the participant's medical record.
- Should the participant continue to be unreachable, he/she will be considered to have withdrawn from the study.

4.7 Screen Failures

A screen failure occurs when a participant who consents to participate in the clinical study is not subsequently entered in the study. A minimal set of screen failure information is required to ensure transparent reporting of screen failure participants to meet the Consolidated Standards of Reporting Trials (CONSORT) publishing requirements and to respond to queries from regulatory authorities. Minimal information includes date of informed consent, demography, reason for screen failure, eligibility criteria and any SAE.

5 STUDY PROCEDURES

5.1 Study Schedule

If the COVID-19 pandemic prevents participants from coming to the site, participants can have their study visit assessments performed remotely as judged appropriate by the Investigator. This must be discussed with the Sponsor before being implemented. In such a case, the Investigator will perform a telemedicine visit and will make every effort, where applicable, to contact the participant's general practitioner or specialist physician to ensure all important medical information and safety event(s) occurring since the last visit are collected. Guidance on how to collect protocol-planned assessments will be provided to the Investigator in a separate document. Such document will be filed in the trial master file. The IEC/IRBs will be notified of the changes as applicable locally. Of note, as the adapted visit deviates from the regular protocol plan, the changes will be recorded as protocol deviations related to COVID-19.

Main study

The schedule of procedures and assessments to be performed during the study is summarised in [Table 1](#).

Table 1 Schedule of Assessments

	Screening Visit		Month 3	Month 6
	Day -28 to Day -1 Prior to Treatment	Day 1	Day 91	Day 182 (EOS/Early Withdrawal)[t]
Study procedures [a]			±3 days	±3 days
Informed consent/assent [b]	X			
Eligibility check [c]	X	X		
Demography	X			
Medical and surgical history	X			
PK samples[d]		X	X	X
Basal LH and FSH [e]	X		X	X
GnRH test with samples for LH and FSH [f]	X		X	X
Oestradiol or testosterone samples [g]	X		X	X
Pubertal Stage (Tanner method) [h]	X			X
Auxological parameters [i]	X		X	X
Bone age and chronological age [j]	X			X
Gonad development [k]	X			X
Body weight [l]	X		X	X
Adverse events [m]	X	X	X	X
Pregnancy test [n]	X			X
Clinical laboratory tests [o]	X		X	X
Physical examination and vital signs [p]	X	X	X	X
Prior and concomitant medications [q]	X	X	X	X
Study drug administration [r]		X	X	
Local tolerability [s]		X	X	

BMI=Body mass index; eCRF=electronic case report form; EOS=End of Study; FSH=Follicle-stimulating hormone; GnRH=Gonadotropin-releasing hormone; IEC=Independent Ethics Committee; IRB=Institutional Review Board; LH=Luteinising hormone; PK=pharmacokinetic

Footnotes to Schedule of Assessments

- a Study procedures to be done before dosing except local tolerability and post-dose PK
- b Informed consent/assent to be performed by parent/legal guardian and by children if determined by local IRB/IEC requirements.
- c Eligibility check of inclusion and exclusion criteria to occur at Screening and prior to dosing on Day 1. All subjects should receive brain MRI to confirm CPP and check for tumours at screening, unless they have available brain MRI scans within 6 months for site to verify.

- d PK Samples on Day 1 to be taken predose and at 4 hours post-injection (\pm 2-hour window); PK sample at Month 3 visit to be taken predose; PK sample at the Month 6 EOS/early withdrawal visit.
- e Basal LH and FSH samples to be drawn before GnRH test. Blood sampling should be taken at approximately the same time of day during each visit.
- f GnRH test samples for LH and FSH concentrations will be collected at 30, 60 and 90 minutes (\pm 5 minutes at each timepoint) after the GnRH test. The LH and FSH samples will all be taken before injection of triptorelin, if applicable (e.g. Month 3 visit).
- g Oestradiol and Testosterone samples for girls and boys, respectively.
- h Tanner pubertal stage as defined in [Appendix 1](#).
- i Auxological parameters including height, growth velocity, weight, BMI will be assessed.
- j Bone Age by Greulich and Pyle method.
- k Gonad development uterine length in girls or testicular volume in boys assessed by type B ultrasound.
- l Body weight participants should weigh \geq 20 kg on inclusion in the study.
- m Adverse events will be collected up to and including the Month 6 visit (i.e. Day 182 \pm 3 days)
- n Pregnancy test for female participants only. Girls who have entered menarche must have a negative pregnancy test prior to the start of study treatment and should not be at risk of pregnancy throughout the study period. Local urine testing will be standard for the protocol unless serum testing is required by local regulation or IRB/IEC before drug treatment for all female participants of childbearing potential and if clinically indicated thereafter.
- o Clinical laboratory tests including chemistry, haematology and urinalysis. In case of abnormal blood glucose as per Investigator's judgement, repetition of these tests will be performed before the first injection.
- p Physical examination and vital signs blood pressure and heart rate.
- q Prior and concomitant medications assessed at every visit
- r Study drug administration following all other assessments, apart from PK samples on Day 1.
- s Local tolerability Measured by tenderness, redness, bruising, erythema, swelling, rash, pain, itching, induration, haematoma, ulceration or necrosis. To be assessed at injection and 2 hours post injection.
- t EOS/Early Withdrawal For participants who do not have a final visit within 3 months (i.e. up to Day 182 \pm 3 days) after their last triptorelin dose, efficacy evaluations (including PK sampling) will not be performed. Data from any efficacy evaluations performed after this time will not be collected on the eCRF.

Extension phase

The schedule of procedures and assessments to be performed during the extension study is summarised in [Table 2](#).

Table 2 Schedule of Assessments in Extension Phase

	Extension phase Baseline	Month 9	Month 12
	Day 1 (day 182 - Month 6)	Day 271	Day 365 (EOEP/Early Withdrawal) [h]
Study procedures [a]		±3 days	±3 days
Informed consent/assent [a]	X		
Basal LH and FSH		X	X
GnRH test with samples for LH and FSH [b]			X
Oestradiol or testosterone samples		X	X
Pubertal Stage (Tanner method)			X
Auxological parameters [c]		X	X
Bone age and chronological age [d]			X
Gonad development [e]			X
Adverse events	X	X	X
Pregnancy test			X
Clinical laboratory tests [f]		X	X
Physical examination and vital signs		X	X
Prior and concomitant medications		X	X
Study drug administration	X	X	
Local tolerability [g]	X	X	

BMI=Body mass index; eCRF=electronic case report form, EOEP=End of Extension Phase; FSH=Follicle-stimulating hormone; GnRH=Gonadotropin-releasing hormone; IEC=Independent Ethics Committee; IRB=Institutional Review Board; LH=Luteinising hormone

Footnotes to Schedule of Assessments

a Informed consent/assent to be performed by parent/legal guardian and by children if determined by local IRB/IEC requirements.

b GnRH test samples for LH and FSH concentrations will be collected at 30, 60 and 90 minutes (±5 minutes at each timepoint) after the GnRH test. The LH and FSH samples will all be taken before injection of triptorelin, if applicable.

c Auxological parameters including height, growth velocity, weight, BMI will be assessed.

d Bone Age by Greulich and Pyle method.

e Gonad development uterine length in girls or testicular volume in boys assessed by type B ultrasound.

f Clinical laboratory tests including chemistry, haematology and urinalysis.

g Local tolerability Measured by tenderness, redness, bruising, erythema, swelling, rash, pain, itching, induration, haematoma, ulceration or necrosis to be assessed at injection.

h EOEP/Early Withdrawal For participants who do not have a final visit within 3 months (i.e. up to Day 365+3 days) after their last triptorelin dose, efficacy evaluations will not be performed. Data from any efficacy evaluations performed after this time will not be collected on the eCRF.

5.2 Study Visits

For a detailed list of procedures at each visit, see [Table 1](#) and [Table 2](#).

5.2.1 *Procedures for the Screening Visit (Day -28 to Day -1 Prior to Treatment) and Enrolment*

A signed and dated informed consent form will be obtained from each parent/legal guardian and a signed and dated assent form will be obtained from each participant before any screening procedures, according to local IRB/IEC requirements. Evaluations obtained as part of routine medical care and performed during the Screening period may be used in place of the study-specific evaluations. Parents/legal guardians will acknowledge and agree to the possible use of this information for the study by giving informed consent.

After informed consent is obtained, screened participants will be allocated a participant number. All screened participants must be identifiable throughout the study. The Investigator will

maintain a list of participant numbers and names to enable records to be found at a later date if required. Each Investigator will also maintain a record of all participants screened in the study (i.e. who signed the informed consent form).

Under no circumstances will participants be screened more than once.

Following confirmation of eligibility for the study, participants will be given a treatment number.

The participant's eligibility for the study will be checked at the Screening visit (based on the inclusion and exclusion criteria presented in Section 4.1 and Section 4.2, respectively) and the assessments described in [Table 1](#) will be performed.

5.2.2 Procedures During the Treatment Phase of Study (Day 1 and Month 3)

The participant's eligibility for the study will be checked again at Day 1 visit (based on the Inclusion and Exclusion criteria presented in Section 4.1 and 4.2, respectively) before the other assessments listed in [Table 1](#).

Participants will be admitted at the clinical site on the morning of Day 1 and the Month 3 visit and the assessments described in [Table 1](#) will be performed. Study drug administration will follow after the other assessments, apart from any post-dose PK samples and local tolerability.

5.2.3 Procedures Following Study Treatment (Month 6, End of Main Study or Early Withdrawal Visit)

Participants who complete the main study will perform final procedures and assessments at the final visit (Month 6). Participants who withdraw from the study before the completion of the evaluation period will be invited to attend an Early Withdrawal visit to perform early discontinuation procedures and assessments (as in [Table 1](#)).

For participants who do not have a final visit within 3 months (i.e. up to Day 182±3 days as in [Table 1](#)) after their last triptorelin dose, efficacy evaluations should not be performed. Data from any efficacy evaluations performed after this time will not be collected on the eCRF.

Participants with ongoing AEs or clinically significant laboratory test abnormalities (as determined by the Investigator) will be monitored as described in Section 8.1.4 and Section 8.1.2.4, respectively. The AEs will be collected up to 3 months after the date of the last injection.

5.2.4 Procedures During the Extension Phase (Month 6, Month 9 and End of Extension Phase Visit)

At the end of the main study, participants who are still benefiting from treatment (i.e. not progressing) and who have not experienced any unacceptable safety issues, will have the option to continue to receive triptorelin every 3 months in the 6-month extension phase.

The participant's eligibility for the extension phase will be checked at Extension Phase Day 1 visit (Month 6) (based on the Inclusion criteria presented in Section 4.3, respectively). The Extension Phase Day 1 visit will correspond to the End of main Study Visit.

Participants will be admitted at the clinical site on the morning of Month 6, Month 9 and Month 12 visit and the assessments described in [Table 2](#) will be performed. Study drug administration will follow after the other assessments on the Month 6 and Month 9 visits, apart from any post-dose PK samples and local tolerability.

For participants who do not have a final visit within 3 months (i.e. up to Day 365±3 days as in [Table 2](#)) after their last triptorelin dose, efficacy evaluations should not be performed. Data from any efficacy evaluations performed after this time will not be collected on the eCRF.

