8 ASSESSMENT OF SAFETY

8.1 Adverse Events

All AEs will be monitored from the time the participant gives informed consent until the EOS visit, or EOEP visit for those enrolled in the extension phase, (see Section 3.8 for definition of the study duration) and will be elicited by direct, non-leading questioning. Further details about AE reporting can be found in Section 8.1.2.

8.1.1 *Definition of an Adverse Event*

These definitions include events occurring from the time the participant gives informed consent until the end of the study (as defined in Section 3.8).

AE Definition:

- An AE is any untoward medical occurrence in a clinical study participant, temporally associated with the use of study intervention, whether or not considered related to the study intervention.
- NOTE: An AE can therefore be any unfavourable and unintended sign (including an abnormal laboratory finding), symptom, or disease (new or exacerbated) temporally associated with the use of study intervention.

Events Meeting the AE Definition:

- Any abnormal laboratory test results (haematology, clinical chemistry, or urinalysis) or other safety assessments (e.g. ECG, radiological scans, vital signs measurements), including those that worsen from baseline, considered clinically significant in the medical and scientific judgment of the investigator (i.e. not related to progression of underlying disease).
- Exacerbation of a chronic or intermittent pre-existing condition including either an increase in frequency and/or intensity of the condition.
- New condition detected or diagnosed after study intervention administration even though it may have been present before the start of the study.
- Signs, symptoms, or the clinical sequelae of a suspected intervention- intervention interaction.
- Signs, symptoms, or the clinical sequelae of a suspected overdose of either study intervention or a concomitant medication. Overdose per se will not be reported as an AE/SAE unless it is an intentional overdose taken with possible suicidal/self-harming intent. Such overdoses should be reported regardless of sequelae.
- “Lack of efficacy” or “failure of expected pharmacological action” per se will not be reported as an AE or SAE. Such instances will be captured in the efficacy assessments. However, the signs, symptoms, and/or clinical sequelae resulting from lack of efficacy will be reported as AE or SAE if they fulfil the definition of an AE or SAE.

Event NOT Meeting the AE Definition:

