The Investigator must instruct all female participants who have already had menophaenia/menarche to inform them immediately should they become pregnant during the study. The Investigator should counsel the participant, discuss the risks of continuing with the pregnancy and the possible effects on the foetus. Monitoring of the participant should continue until conclusion of the pregnancy, which may involve follow-up after the participant's involvement in the study has ended.

Pregnancies with a conception date within 3 months after the participant's last dose of study medication must also be reported to the Investigator for onward reporting to the Sponsor.

If the Investigator becomes aware of a pregnancy occurring in the partner of a participant participating in the study, this should be reported to the Sponsor as described above. Pregnancies in the partner with a conception date until 3 months after participant's last dose of

study medication should be reported after the partner has given written consent and the partner should be counselled and followed as described above. Monitoring of the partner should continue until conclusion of the pregnancy.

8.1.7 *Deaths*

All AEs resulting in death during the study period (from first injection until 3 months after the date of the last study drug administration), must be reported as an SAE within 24 hours of the Investigator's knowledge of the event.

The convention for recording death is as follows:

- AE term: lead cause of death (e.g. multiple organ failure, pneumonia, myocardial infarction)
- Outcome: fatal.

The **only exception** is if the cause of death is unknown (i.e. sudden or unexplained death), in which case the AE term may be reported as "death" or "sudden death".

8.1.8 *Discontinuation/Withdrawal due to Adverse Events/Serious Adverse Events*

Discontinuation/withdrawal due to AEs should be distinguished from discontinuation/withdrawal due to insufficient response to triptorelin (see Section 4.4).

If triptorelin is discontinued due to an SAE, it must be reported immediately to the Sponsor's designated representative (see Section 8.1.5).

In all cases, the Investigator must ensure that the participant receives appropriate medical follow-up (see Section 8.1.4).

8.1.9 *Reporting to Competent Authorities/Independent Ethics Committees/Institutional Review Boards/Other Investigators*

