A TEAE is defined as any AE that occurs during the active phase of the study (between the start date of the treatment and the end of study treatment) if:

- It was not present prior to receiving the first dose of triptorelin, or
- It was present prior to receiving the first dose of triptorelin but the grade increased or became serious during the active phase of the study, or
- It was present prior to receiving the first dose of triptorelin, the grade/seriousness is the same but the causality changed to “related” during the active phase of the study.

All TEAEs will be flagged in the AE listings.

Summary incidence tables will be provided, classified by SOC, PT and associated NCI-CTCAE worst grade. In the event of multiple occurrences of the same AEs being reported for the same participant, the maximum intensity (Grade 5 > Grade 4 > Grade 3 > Grade 2 > Grade 1 > missing > not applicable) will be chosen. All AEs will be collected up to the EOS visit (see [Table 1](#) for schedule), or EOEP visit for those enrolled in the extension phase.

Concomitant medication will be coded by using World Health Organization Drug Dictionary (WHO-DD) version (current version in use at the start of the study) and will be summarised with the number and percentage of participants receiving concomitant medication by drug class and preferred drug name.

Haematological and biochemical toxicities will be recorded and graded according to the NCI-CTCAE criteria, where available. The NCI-CTCAE Grades 3 and 4 haematology and biochemistry variables will be listed by participant and by visit.

Actual values and changes from Baseline in clinical laboratory tests, physical examinations and vital signs will be summarised using descriptive statistics at each visit. For laboratory data, abnormal values will be flagged in the data listings and a list of clinically significant abnormal values will be presented. Shift tables using the worst on-treatment grade will be presented for the number and percentage of participants with NCI-CTCAE grades.

11.4.7 *Efficacy and Safety Evaluations (Extension Phase)*

A separate analysis on efficacy and safety endpoints will be performed considering the extension phase duration, a period of an additional 6 months, lasting until the End of Extension Phase Visit at Month 12.

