### 5.8.3 *Adverse Event*

All adverse events (AEs) recorded in the eCRF will be coded using the latest version of MedDRA dictionary in effect within IPSEN at the time of the database lock. AEs will be classified as treatment-emergent AEs (TEAEs) according to the rules below:

- Events with start date on or after the date of first IMP administration and up to the EOS or 185 days after first dose days which comes first.
- Events whose CTCAE grade worsens on or after the date of first IMP administration,
- Events whose causality changes to “Related” on or after the date of first IMP administration,
- Refer to appendix [Partial/Missing Date Convention A2](#) for handling of partial date. In the case where it is not possible to define an AE as treatment emergent or not, the AE will be classified by the worst case; i.e. treatment emergent.

Tabular summaries will be presented by gender. Summaries will include the number and percentage of participants and classified by primary system organ class and preferred term. The following summaries will be reported for AEs, TEAE regardless of drug relationship, TEAE related to study drug, TEAE grade 3 and above regardless of drug relationship, TEAE grade 3 and above related to study drug, serious AEs (SAEs), AE leading to study drug discontinuation, and AE leading to death:

- An overview table summarizing the number and percentage of participants with at least one of the following AEs: any AE; any TEAE; SAE, treatment emergent SAE, treatment-related TEAE, treatment emergent-related SAE, Non-serious TEAEs, TEAE leading to treatment discontinuation; TEAE leading to discontinuation from the study, CTCAE Grade  $\geq 3$  TEAE, Death, TEAE leading to death,
- A summary of the number and percentage of participants reporting a TEAE by gender, SOC and PT,
- A summary of the number and percentage of participants reporting a SAE by gender group and PT,
- A summary of the number and percentage of participants reporting a Serious TEAE by gender group and PT,
- A summary of the number and percentage of participants reporting a treatment-related Serious TEAE by gender group and PT,
- A summary of the number and percentage of participants reporting a TEAE leading to treatment discontinuation by gender group and PT,
- A summary of non-serious TEAE by gender group, SOC and PT,
- A summary of TEAE by gender group and PT,
- A summary of the number and percentage of participants reporting a TEAE by gender group, CTCAE grade, SOC and PT,

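### The protocol gives conflicting ends for AE collection; for early withdrawals they can differ by up to about 91 days, and the SAP's new-onset TEAE cut-off may not match the rule followed

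*Protocol*

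**What the plan says.** Four places in the protocol set an end for AE collection:

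- Section 5.2.3, which covers the Month 6, end-of-main-study and Early Withdrawal visits: "The AEs will be collected up to 3 months after the date of the last injection".
- Section 5.1, Table 1 footnote m: "Adverse events will be collected up to and including the Month 6 visit", which the footnote equates with Day 182 ± 3 days.
- Section 8.1: "All AEs will be monitored from the time the participant gives informed consent until the EOS visit", with the EOEP visit substituted for children in the extension.
- Section 11.4.6: "All AEs will be collected up to the EOS visit", with the same substitution.

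Section 8.1.7 also uses a 3-month window, for fatal AEs only: "from first injection until 3 months after the date of the last study drug administration".

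None of the three visit-based rules names the Early Withdrawal visit. Table 1 gives it and EOS one shared column, "Day 182 (EOS/Early Withdrawal". Section 3.8 ends participation at the last visit and labels that visit EOS. The withdrawal text in Section 4.4 refers to evaluations at the EOS visit. Section 3.1, however, places EOS at Month 6 and mentions the Early Withdrawal visit separately. No section fixes the day of the Early Withdrawal visit or schedules a contact after it. For the extension, Table 2 has an AE row without a footnote on when collection ends, and Section 5.2.4 states no AE window.

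For analysis, SAP 5.8.3 counts a new event as treatment-emergent if it starts on or after the first administration and "up to the EOS or 185 days after first dose days which comes first". Its rules for grade worsening and for causality changing to related carry no end date. Protocol Section 11.4.6 ends the TEAE window at the end of study treatment, which it does not define. SAP 2.6 reports no change from the protocol's statistical section.

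**The concern.** A site handling a child who leaves early cannot tell from the protocol when to stop collecting AEs. One rule runs for three months after the injection. Another, on the most natural reading of the shared Table 1 column, stops on the day of the withdrawal visit. A third, read literally, runs to Day 182 whatever the number of injections. Sites may reasonably differ.

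The SAP adds a second layer. If the withdrawal visit is EOS, an event that Section 5.2.3 requires the site to collect after that visit falls outside the new-onset TEAE window. The child stays in the Safety population, which requires only one dose and one post-baseline safety assessment, so an omitted event can lower a TEAE percentage but cannot raise it. TEAE incidence is the first safety endpoint listed in Section 3.2.3.

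**Working it through.** **Inputs.** Main-phase injections on Day 1 and Day 91 ± 3, and EOS on Day 182 ± 3 (Table 1). Month 9 injection on Day 271 ± 3, and EOEP on Day 365 ± 3 (Table 2). Planned enrolment 32 with 10% dropout (Section 11.2). Assumption: 3 months = 91 days, the Day 91 to Day 182 interval.

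**Step 1, the plan's own figure.** Section 5.2.3 equates 3 months after the last dose with Day 182 ± 3. Check: 91 + 91 = 182; 88 + 91 = 179; 94 + 91 = 185. This reproduces.

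**Step 2, completers.** On schedule the gap is 0 days. Within the visit windows the rules can part slightly:

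- Injection Day 88, visit Day 185: the 3-month end is Day 179, which is 185 − 179 = 6 days before the visit.
- Injection Day 94, visit Day 179: the 3-month end is Day 185, which is 6 days after the visit.
- Extension, injection Day 271: 271 + 91 = 362, against EOEP Day 362 to 368, so 0 to 6 days before the visit.
- Extension, injection Day 268: 268 + 91 = 359, up to 368 − 359 = 9 days before the visit.

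**Step 3, early withdrawals, if the withdrawal visit counts as EOS.** Gap = (last injection + 91) − visit day = 91 − w, where w is days from last injection to visit:

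| w (days) | gap (days) |
|---|---|
| 0 | 91 |
| 7 | 84 |
| 30 | 61 |
| 60 | 31 |
| 90 | 1 |

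**Step 4, footnote m read literally.** For a child given only the Day 1 injection, the 3-month end is 1 + 91 = Day 92. Footnote m runs to Day 182, which is 182 − 92 = 90 days longer. No follow-up is lost on this reading, but it still contradicts Section 5.2.3.

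**Step 5, what else keeps events reportable.**

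- Section 4.4: an AE or laboratory abnormality that causes withdrawal is monitored until one of several stated outcomes, such as resolution or stabilisation.
- Section 8.1.4: AEs persisting after discontinuation are followed until resolved or stable.
- Section 8.1.5: suspected-related AEs and SAEs are reportable after study completion, with no end date.
- Section 8.1.6: pregnancies conceived within 3 months of the last dose.
- Section 8.1.7: fatal AEs within 3 months of the last dose.

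What remains exposed in collection is new-onset, non-fatal AEs, including non-fatal SAEs, that are not judged related and start after the withdrawal visit.

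**Step 6, the TEAE tables.** The provisions in Step 5 govern reporting, not the SAP's new-onset rule. If the withdrawal visit is EOS, that date comes before the 185-day limit and sets the cut-off. Any new event after it, related or not, is outside the new-onset TEAE definition.

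**Step 7, scale.** 0.10 × 32 = 3.2, so about 3 children at the planned dropout rate. With 32 in the Safety population (assumed), one omitted child changes a TEAE percentage by 1/32 = 3.1 points, provided that child has no other event counted in that row.

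**The case against.** The strongest reply is that the rules may be one end-point phrased several ways. Section 5.2.3 and Table 1 footnote t themselves equate 3 months after the last dose with Day 182 ± 3. None of the visit-based rules names the withdrawal visit, and footnote m read literally would follow a child withdrawn after one dose for longer, not shorter. This stands as a limit on the point: the loss of follow-up depends on treating the Early Withdrawal visit as EOS. Table 1, Section 3.8 and Section 4.4 support that reading but do not state it. The conflict itself does not depend on it, because the literal reading also disagrees with Section 5.2.3.

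A reader might infer that early withdrawals lose three months of safety data in general. The documents do not support that. About 91 days is a ceiling reached only when the visit falls at or just after an injection, and several classes of event stay reportable, including those that caused the withdrawal.

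A reader might also infer that no later event could ever be treatment-emergent. That is too strong as well: the SAP's worsening and causality-change rules have no end date.

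Finally, it can be objected that simply adopting 3 months after the last injection would shorten collection for some completers. Step 2 of the working shows this is correct, and the fix has to allow for it.

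**Conclusion.** The conflict is in the current protocol text and should be reconciled. For completers it is a matter of days. For early withdrawals the ends can differ by up to about 91 days, taking 3 months as 91 days and the withdrawal visit as EOS. About 3 children would be affected at the planned dropout rate, which is a sample-size assumption; the documents do not say when dropouts would occur.

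Two consequences should be kept apart. In collection, only new-onset, non-fatal events not judged related are exposed. In analysis, on the same reading, every new event after the withdrawal visit is outside the SAP's new-onset TEAE window, even when collected. The protocol's own TEAE window does not settle this. The Synopsis counts two injections as six months of treatment, but nothing says when treatment ends for a child who stops early.

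A claim that TEAE incidence will be biased downward goes further than the documents allow. The direction of any error is clear, but its occurrence depends on events falling in the gap, and its size cannot be estimated from the plan.

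**What to change.** State one end for AE collection, saying explicitly what applies to early withdrawals, and use it in Section 5.2.3, Table 1 footnote m, Table 2, Section 8.1 and Section 11.4.6. Then align the TEAE windows in protocol Section 11.4.6 and SAP 5.8.3 with it, and define the end of study treatment or drop the term. If the 3-month rule of Section 5.2.3 is kept, word it as the final visit or 3 months after the last injection, whichever is later, so that no completer loses follow-up. Which window to use is the sponsor's decision.

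While SAP 5.8.3 is open, give the extension its own TEAE limit: SAP 5.9.2 carries the main-phase AE analysis over unless otherwise specified, and the 185-day limit does not fit events up to Month 12.

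The cost is wording in the protocol and SAP. If the chosen rule runs past the withdrawal visit, it also needs a contact for about 3 children at the planned dropout rate. That contact is a new procedure and applies only where consent for it remains and the family can be reached.
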